8.5.3. Plasma PK [REDACTED] Bioanalysis

Concentrations of ubrogепant in plasma [REDACTED] es will be determined using validated and qualified liquid chromatography-tandem mass spectrometry methods, respectively.

8.6. Pharmacodynamics

Pharmacodynamic parameters are not evaluated in this study.

8.7. Genetics

Genetics are not evaluated in this study.

8.8. Biomarkers and Other Assessments

Measurement of CGRP concentrations in plasma [REDACTED] will be attempted from the PK samples at the timepoints specified in Sections 8.5.1 and 8.5.2. These samples will be collected, processed, and shipped as described in Sections 8.5.1 and 8.5.2 above.

Biomarker blood samples should be drawn at the nominal times specified above, relative to the dosing time, and the actual time of the blood draw must be recorded in the source documents and eCRFs. Samples taken more than ± 5 minutes from the nominal time will be noted as protocol deviations, and the reason for deviation must be recorded in the source documents and eCRFs. Predose samples must be drawn within 30 minutes of the dosing time.

8.9. Health Economics/Medical Resource Utilization and Health Economics

Health economics/Medical resource utilization and health economics parameters are not evaluated in this study.

9. Statistical Considerations

9.1. Statistical Hypotheses

Not applicable.

9.2. Sample Size Determination

This is a study to evaluate the safety, tolerability and PK of ubrogapant when co-administered with CGRP MABs. Although the sample size is not based on a statistical calculation, inclusion of 40 participants (20 participants in each part [REDACTED]) is considered reasonable to achieve the objectives of the study.

9.3. Populations for Analyses

The analysis populations will consist of participants as defined below:

Table 9-1 Analysis Populations

Population	Definition
Pharmacokinetic (PK1) [REDACTED]	All participants who have evaluable PK parameters of ubrogapant for both ubrogapant alone and ubrogapant in combination with erenumab or galcanezumab [REDACTED]
Safety	All participants who received ≥ 1 administration of study intervention

9.4. Statistical Analyses

The SAP will be developed and finalized before database lock and will describe the participant populations to be included in the analyses and procedures for accounting for missing, unused, and spurious data. This section is a summary of the planned statistical analyses of PK and safety data.

9.4.1. Pharmacokinetic Analyses

The principal parameters describing the PK of ubrogapant will be derived from plasma concentrations using noncompartmental analysis with the software program [REDACTED]. Plasma concentrations below the limit of quantification will be treated as zero for all PK calculations. The actual sampling times will be used in the calculations of PK parameters in this study.

9.4.1.1. Pharmacokinetic Parameters

The following PK parameters for ubrogapant will be calculated based on standard [REDACTED] equations: area under the plasma concentration versus time curve from time 0 to time t (AUC_{0-t}) and from time 0 to infinity ($AUC_{0-\infty}$), maximum plasma drug concentration

Ubrogепant (AGN-241688)

(C_{max}), time of maximum plasma drug concentration (T_{max}), terminal elimination rate constant (λ_z), terminal elimination half-life ($T_{1/2}$), apparent total body clearance of drug from plasma after extravascular administration (CL/F), and apparent volume of distribution during the terminal phase after extravascular administration (V_z/F).

The AUC_{0-t} will be calculated by using the linear-log trapezoidal rule.

Estimates of $T_{1/2}$ will be calculated based on λ_z . The λ_z will be determined by performing a regression analysis on the terminal linear phase of semilogarithmic plots of individual ubrogепant concentration-time data using a minimum of three concentration-time points in the elimination phase excluding C_{max} . λ_z will be considered to be valid if $r^2 > 0.8$.

9.4.1.2. Statistical Analyses of Pharmacokinetic Data

Details of the statistical analyses of ubrogепant PK data (concentrations and parameters) will be described in the PK analysis plan finalized before database lock.

Descriptive statistics will be provided for all PK parameters of ubrogепant for participants in the Pharmacokinetic PK1 population by study part and by study intervention. PK parameters (C_{max} , AUC_{0-t} , and $AUC_{0-\infty}$) for ubrogепant will be compared using a linear mixed-effects model with study intervention as fixed effect and participant as a random effect.

Statistical analysis will be based on log-transformed values for the C_{max} and AUC parameters of ubrogепant. The 2-sided 90% CI for each study part will be constructed for the ratio of least squares geometric means of C_{max} , AUC_{0-t} , and $AUC_{0-\infty}$ of ubrogепant in combination with CGRP MAB on Day 12 versus ubrogепant alone on Day 1. No effect of co-administration with CGRP MABs on the PK of ubrogепant will be concluded if the 90% CIs for the ratios of ubrogепant PK parameters for test study intervention versus reference study intervention are within the limits of 80% to 125%.

Descriptive statistics will be reported for the plasma concentrations of ubrogепant by study part at each nominal time point for all participants in the Pharmacokinetic PK1 population. [REDACTED]

9.4.2. Safety Analyses

The safety analysis will be performed using the safety population and will be fully defined in the SAP. The safety parameters will include AEs, clinical laboratory parameters, vital signs, and ECG parameters. Safety analyses will be reported for each study part separately.

9.4.2.1. Adverse Events

An AE will be considered a TEAE if the AE began or worsened (increased in severity or became serious) on or after the date (and time, if known) of the first dose of study intervention. However, an AE that occurs more than 30 days after the last dose of study intervention will not be counted as a TEAE.

An AE will be considered a TESAE if it is a TEAE that additionally meets any SAE criterion.

The number and percentage of participants with TEAEs in each study intervention group will be tabulated by system organ class and preferred term and by system organ class, preferred term, and severity. The number and percentage of participants with study intervention-related TEAEs in each study intervention group will be tabulated by system organ class and preferred term.

If more than 1 AE is coded to the same preferred term for the same participant, the participant will be counted only once for that preferred term using the most severe and most related occurrence for the summarizations by severity and by relationship to study intervention.

Summary tables will be provided for participants with TESAEs and participants with TEAEs leading to discontinuation if 5 or more participants reported such events. Listings of all AEs, SAEs, and AEs leading to discontinuation by participant will be presented.

The definitions of an AE and SAE can be found in [Appendix 3](#).

An AE will be assigned to the study intervention when it occurred on or after the first dose of the study intervention or the subsequent washout period in which the AE occurred, before the first dose of the next study intervention. An AE will be assigned to the last study intervention of the study intervention sequence if it occurred on or after the first dose of the last study intervention administration.

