4.1. Overall Design

This study will be a Phase 1b, 2-part, multi-center, open-label, fixed-sequence drug interaction study in 40 male and female participants who have been diagnosed with migraine for at least 1 year and are aged 18 through 50 years. In Part 1, 20 participants will receive a single oral dose of 100 mg ubrogепant alone (Study Intervention A) on Day 1, a single SC injection of 140 mg erenumab alone (Study Intervention B) on Day 8, followed by once daily oral doses of 100 mg ubrogепant on Days 12 through 15 (Study Intervention D) under fasted conditions. Similarly, in Part 2, a separate cohort of 20 participants will receive a single oral dose of 100 mg ubrogепant alone (Study intervention A) on Day 1, 2 consecutive SC injections of 120 mg galcanezumab alone (Study intervention C) on Day 8, followed by once daily oral doses of 100 mg ubrogепant on Days 12 through 15 (Study Intervention D) under fasted conditions.

If all doses are well tolerated, the duration of participation in the study will be 46 ± 3 days (Day -1 through the safety Follow-up Visit on Day 45), not including the Screening Visit.

- Duration:
 - Screening: Up to 21 days (Day -21 to Day -1)
 - Intervention Period: Up to a total of 17 days (Day -1 to Day 16)
 - Follow-up period: 30 (± 3) days after the last dose

- PK and Biomarker Sampling

In Part 1 and Part 2, PK blood samples for the analysis of ubrogепant and CGRP concentrations will be collected at 0 hour (predose), 0.5, 1, 1.5, 2, 3, 4, 5, 6, 8, 12, 14, and 24 hours postdose on Days 1 and 12.

[REDACTED]

- Safety Measurements

The safety and tolerability profiles when ubrogепant and erenumab or ubrogепant and galcanezumab are co-administered and when each study intervention is administered alone in participants with migraine will be evaluated by clinical assessment of AEs, physical examinations, safety 12-lead ECGs, standard laboratory safety tests (hematology, serum chemistry, and urinalysis), and by measurements of vital signs at specified time points after each study intervention.

- Number of Participants

A total of 40 participants at up to 3 sites in the United States will be enrolled in the study; 20 participants in Part 1 and a separate cohort of 20 participants in Part 2. Part 1 and Part 2 will enroll in parallel. [REDACTED]

██████████. Participants who prematurely discontinue from the study may be replaced at the discretion of the sponsor.

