6.3. Measures to Minimize Bias: Randomization and Blinding

Participants will be randomized to 1 of 2 parts: Part 1 or Part 2. Participants randomized to Part 1 will receive Study Intervention A on Day 1, Study Intervention B on Day 8, and Study Intervention D once daily on Days 12 through 15. Participants randomized to Part 2 will receive Study Intervention A on Day 1, Study Intervention C on Day 8, and Study Intervention D once daily on Days 12 through 15.

[REDACTED]

[REDACTED]

This is an open-label study; no blinding of assigned study intervention will occur.

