- Study center staff will admit participants into a nonsmoking environment on Days -1, and 7. Participants will remain in the study center until 24 hours following study intervention administration on Day 1 and on Days 7 through 16 for a total of 11 overnight stays (2 overnight stays on Days -1 and 1; and 9 overnight stays on Days 7 through 15). Participants will be released from the study center on Day 2 after the 24-hour postdose PK blood draw and on Day 16 after completion of the 96-hour or EOD assessments. Participants will be administered doses of Study Intervention B or Study Intervention C on Day 8, and ubrogепant doses (Study Intervention A and D) on Days 1 and 12 through 15 at the study center.

- The amount of blood collected from each participant over the duration of the study will be approximately 194 mL. Repeat or unscheduled samples may be taken for safety reasons or for technical issues with the samples.

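### The by-intervention AE table sets a combination window of up to 33 days beside 4- and 7-day 'alone' windows; splitting the combination column at Day 16 would make it easier to read

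*Protocol*

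**What the plan says.** Protocol 6.3 fixes the dosing days. A Part 1 participant "will receive Study Intervention A on Day 1, Study Intervention B on Day 8, and Study Intervention D once daily on Days 12 through 15"; Part 2 is the same with C in place of B.

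Protocol 9.4.2.1 then sets three rules:

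- **Assignment.** An AE belongs to an intervention from its first dose, through the washout, until the next intervention's first dose. For the final one, D, the rule reads: "An AE will be assigned to the last study intervention of the study intervention sequence if it occurred on or after the first dose". The dose meant is the Day 12 dose of D.
- **Cut-off.** "an AE that occurs more than 30 days after the last dose of study intervention will not be counted as a TEAE".
- **Display.** "The number and percentage of participants with TEAEs in each study intervention group will be tabulated by system organ class and preferred term". Tables by severity and of related TEAEs use the same columns. No window length, sub-period or exposure adjustment is mentioned. The section also promises: "Listings of all AEs, SAEs, and AEs leading to discontinuation by participant will be presented".

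Elsewhere the protocol does separate dosing from follow-up. Section 4.1 ends the intervention period on Day 16 and lists a separate "Follow-up period: 30 (± 3) days after the last dose". Section 8 releases participants "on Day 16 after completion of the 96-hour or EOD assessments". Section 9.4.2.2 presents EOD and Follow-up laboratory values overall, and only interim values by intervention.

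Protocol 9.4 calls itself a summary, and 9.4.2 leaves the full safety analysis to the SAP. The SAP at hand covers PK and biomarkers, and its Section 3 refers safety to a separate plan.

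**The concern.** One secondary objective is to describe safety and tolerability in combination and alone (Protocol 3). The by-intervention TEAE table is the natural place to look for that, and its columns cover very different lengths of time. A participant percentage rises with observation time even when no drug causes anything. A reader who compares D with A and with B or C will therefore tend to see more events under the combination, and the table cannot show whether they arose in the four days of co-dosing or in the following month at home. At stake is a descriptive impression of combination tolerability; no AE test is planned.

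**Working it through.** **1. Check the day count against the protocol's own totals.** There is no Day 0. Day -1 to Day 45 inclusive is 45 + 1 = 46 days (stated: 46). Day -1 to Day 16 is 16 + 1 = 17 (stated: 17). Last dose plus 30 is 15 + 30 = Day 45 (stated Follow-up Visit). A to B or C is 8 - 1 = 7 (stated washout: 7). All agree.

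**2. AE windows, in elapsed days, for participants who complete dosing.**

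- A: 8 - 1 = 7
- B or C: 12 - 8 = 4
- D: 45 - 12 = 33, of which 16 - 12 = 4 are dosing and 45 - 16 = 29 are follow-up; 29/33 = 88%

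In inclusive calendar days D is 34 = 4 + 30, which matches the protocol's 30-day follow-up. The one-day difference does not affect the point. D's window is 33/7 = 4.7 times A's and 33/4 = 8.25 times that of B or C.

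**3. What background events alone would do.** The documents give no background rate. Assume that a given term has incidence p per week of 0.5%, 1%, 2% or 5%, with constant hazard, no drug effect and n = 20. Then h = -ln(1 - p)/7, the probability in a window of d days is 1 - exp(-h·d), and the expected count is 20 times that. At p = 1%, h = 0.001436 per day, so A = 1.00%, B or C = 0.57% and D = 4.63%.

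The probability that D exceeds both other columns is the sum over k of P(D = k)·P(A < k)·P(B or C < k), from independent binomials. For a lead of at least 2, replace k by k - 1 in the last two factors. If AEs in follow-up are recorded at half the confined rate (also an assumption), D's effective window is 4 + 29/2 = 18.5 days.

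| Assumed incidence per week | 0.5% | 1% | 2% | 5% |
|---|---|---|---|---|
| Expected participants, A | 0.10 | 0.20 | 0.40 | 1.00 |
| Expected participants, B or C | 0.06 | 0.11 | 0.23 | 0.58 |
| Expected participants, D | 0.47 | 0.93 | 1.82 | 4.30 |
| D exceeds both | 33% | 51% | 69% | 90% |
| D leads both by at least 2 | 7% | 19% | 41% | 77% |
| D exceeds both, follow-up recorded at half rate | 20% | 32% | 46% | 66% |
| D dosing period only (4 days) exceeds both | 5% | 8% | 12% | 14% |

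The same participants fill all columns, so independence is an approximation. A shared gamma frailty with variance 1 to 3 gives 33-32%, 50-49%, 68-66% and 88-85% for the first probability row, which is little changed.

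**4. Is Day 16 a sensible cut?** Protocol 2.2 gives ubrogepant a half-life of 5 to 7 hours. Assuming mono-exponential decline, 24 hours after the Day 15 dose the fraction left is 0.5^(24/5) = 3.6% to 0.5^(24/7) = 9.3%. Co-exposure is therefore largely over by EOD. The antibodies, with half-lives of 28 days (erenumab) and 27 days (galcanezumab), are still present.

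**The case against.** The strongest reply is that the safety SAP has not been seen. Protocol 9.4 is only a summary, and a split by dosing and follow-up is just what a safety SAP would contain. That stands: what is shown is that the protocol rule has no split, not that the plan as a whole lacks one.

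Second, late onsets can be found by hand. With 20 participants per part, the AE listings allow it, and laboratory values at EOD and Follow-up are summarised separately. This also stands and limits the harm, though the tables are what most readers will use. The related-TEAE table has the same unequal columns and depends on open-label causality judgments.

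Third, the probabilities of any excess flatter the point. The pattern of one participant in D and none in the other two columns makes up about 77% of the exceedances at 0.5% per week and 54% at 1%. Participants are confined from Day 7 to Day 16 and are outpatients afterwards, so recording may be thinner in follow-up. Both objections are right, and the lead-of-2 and half-rate rows above answer them. The effect shrinks but stays well above the dosing-period figures.

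Fourth, the long antibody half-lives justify keeping late events under the combination. Agreed. A reader might infer that the assignment rule is wrong, or that events after Day 16 should be credited to the antibody alone. The documents support neither.

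**Conclusion.** The point holds as an inexpensive improvement to one display, between optional and recommended. For participants who complete dosing, nominal elapsed windows are 7, 4 and up to 33 days, and 88% of the last lies after the dosing period. With equal background risk, the combination column is expected to be the highest without any drug effect. How often this shows depends on assumed rates: D leads both other columns by at least 2 participants in 7% to 77% of trials over 0.5% to 5% per week. For rare terms the effect is small. Drug-related events that cluster near dosing would not scale with window length, so the figures apply to background events only.

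A reader might go further and conclude that the safety evaluation is biased or invalid. The documents do not support that: the tables are descriptive, no hypothesis is stated, listings by participant are planned, and the detailed safety plan lies in a document not available here.

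**What to change.** Keep the assignment rule and the main table, so that late AESIs and ALT/AST elevations stay counted under the combination. In Section 9.4.2.1 and the safety SAP:

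- Add one display per study part of D TEAEs by onset: 'dosing period' (first dose on Day 12 to EOD on Day 16) and 'follow-up' (after EOD to 30 days after the last dose). Do not label the second part 'MAB only', given the antibody half-lives. Footnote that a participant may count in both parts, so they need not add up to the D total.
- Footnote the main table: 'Nominal elapsed days for participants who complete dosing: A 7, B or C 4, D up to 33; a participant who stops after A or B/C contributes up to 30 days after the last dose to that column.' Bare column headers of 7 and 4 days would be wrong for early stoppers.
- If the safety SAP already has the split, cross-refer to it.

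The cost is one extra table per part, from onset dates that the TEAE rule already needs. Counts will be small (about 0.06 to 0.58 expected participants per term in D's dosing period under the rates above) and the parts are not additive. A, at 7 days, will still differ from the 4-day columns.

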9.4.2.2. Clinical Laboratory Assessments

Descriptive statistics for clinical laboratory values (in SI units) at baseline, EOD, Follow-up visit, and changes from baseline at each assessment will be presented overall for each clinical laboratory parameter in each part of the study.

Descriptive statistics for interim clinical laboratory values at predose, postdose, and changes from predose at postdose will be presented by study intervention in each part of the study.

The criteria for potentially clinically significant (PCS) laboratory values will be detailed in the SAP. The number and percentage of participants who have PCS postbaseline clinical laboratory values will be tabulated overall for EOD assessment and Safety Follow-up visit and by study intervention for interim assessments. The percentages will be calculated relative to the number of participants who have available non-PCS baseline values and at least 1 postbaseline assessment. The numerator will be the total number of participants mentioned prior with at least 1 PCS postbaseline value. A supportive listing of participants with PCS postbaseline values will be provided for the safety population.

9.4.2.3. Vital Signs

Descriptive statistics for vital signs (systolic and diastolic BP, pulse rate, weight, respiration rate, and temperature) at baseline (screening), EOD, and changes from baseline at EOD will be presented overall in each study part.

Descriptive statistics for interim vital signs (systolic and diastolic BP, pulse rate) at predose, postdose, and changes from predose at postdose will be presented by study intervention in each part of the study.

Vital signs values will be considered to be PCS if they meet both the observed-value criteria and the change-from-baseline-value criteria that will be detailed in the SAP. The number and percentage of participants who have PCS postbaseline vital sign values will be tabulated overall for EOD and by study intervention for interim assessment. The percentages will be calculated relative to the number of participants who have available non-PCS baseline values and at least 1 postbaseline assessment. The numerator will be the total number of participants mentioned prior with at least 1 PCS postbaseline value. A supportive listing of participants with PCS postbaseline values will be provided for the safety population.

9.4.2.4. Electrocardiograms

Descriptive statistics for ECG parameters (heart rate, PR interval, QRS duration, QT interval, and QTc) at baseline, EOD, and changes from baseline at EOD will be presented overall in each study part.

Descriptive statistics for interim ECG parameters at predose, postdose, and changes from predose at postdose will be presented by study intervention in each part of the study.

The criteria for PCS ECG values will be detailed in the SAP. The number and percentage of participants who have PCS postbaseline ECG values will be tabulated overall for EOD and by study intervention for interim assessments. The percentages will be calculated relative to the number of participants who have available non-PCS baseline values and at least 1 postbaseline assessment. The numerator will be the total number of participants mentioned prior with at least 1 PCS postbaseline value. A supportive listing of participants with PCS postbaseline values will be provided for the safety population.

9.5. Interim Analyses

No interim analysis is planned for this study.

9.5.1. Data Monitoring Committee

Not applicable.

10. Supporting Documentation and Operational Considerations

10.1. Appendix 1: Regulatory, Ethical, and Study Oversight Considerations

10.1.1. Regulatory and Ethical Considerations

- This study will be conducted in accordance with the protocol and with the following:
 - Consensus ethical principles derived from international guidelines including the CIOMS International Ethical Guidelines
 - Applicable ICH GCP guidelines
 - Applicable laws and regulations
- The protocol, protocol amendments, ICF, investigator’s brochure, and other relevant documents (eg, advertisements) must be submitted to an IRB by the investigator and reviewed and approved by the IRB before the study is initiated.
- Any amendments to the protocol will require IRB approval before implementation of changes made to the study design, except for changes necessary to eliminate an immediate hazard to study participants.
- The investigator will be responsible for the following:
 - Providing written summaries of the status of the study to the IRB annually or more frequently in accordance with the requirements, policies, and procedures established by the IRB
 - Notifying the IRB of SAEs or other significant safety findings as required by IRB procedures
 - Providing oversight of the overall conduct of the study at the site and adherence to requirements of applicable local regulations, for example 21 CFR, ICH guidelines, the IRB, and European regulation 536/2014 for clinical studies (if applicable)

